8.2 INFORMED CONSENT

The Sponsor's sample Informed Consent Form will be provided to each site. If applicable, it will be provided in a certified translation of the local language. The Sponsor or its designee must review and approve any proposed deviations from the Sponsor's sample Informed Consent Forms or any alternate consent forms proposed by the site (collectively, the "Consent Forms") before IRB/EC submission. The final IRB/EC-approved Consent Forms must be provided to the Sponsor for health authority submission purposes according to local requirements.

If applicable, the Informed Consent Form will contain separate sections for any optional procedures. The investigator or authorized designee will explain to each patient the objectives, methods, and potential risks associated with each optional procedure. Patients will be told that they are free to refuse to participate and may withdraw their consent at any time for any reason. A separate, specific signature will be required to document a patient's agreement to participate in optional procedures. Patients who decline to participate will not provide a separate signature.

The Consent Forms must be signed and dated by the patient or the patient's legally authorized representative before his or her participation in the study. The case history or clinical records for each patient shall document the informed consent process and that written informed consent was obtained prior to participation in the study.

The Consent Forms should be revised whenever there are changes to study procedures or when new information becomes available that may affect the willingness of the patient to participate. The final revised IRB/EC-approved Consent Forms must be provided to the Sponsor for health authority submission purposes.

Patients must be re-consented to the most current version of the Consent Forms (or to a significant new information/findings addendum in accordance with applicable laws and IRB/EC policy) during their participation in the study. For any updated or revised

Consent Forms, the case history or clinical records for each patient shall document the informed consent process and that written informed consent was obtained using the updated/revised Consent Forms for continued participation in the study.

A copy of each signed Consent Form must be provided to the patient or the patient's legally authorized representative. All signed and dated Consent Forms must remain in each patient's study file or in the site file and must be available for verification by study monitors at any time.

Each Consent Form may also include patient authorization to allow use and disclosure of personal health information in compliance with the U.S. Health Insurance Portability and Accountability Act of 1996 (HIPAA). If the site utilizes a separate Authorization Form for patient authorization for use and disclosure of personal health information under the HIPAA regulations, the review, approval, and other processes outlined above apply except that IRB review and approval may not be required per study site policies.

8.3 INSTITUTIONAL REVIEW BOARD OR ETHICS COMMITTEE

This protocol, the Informed Consent Forms, any information to be given to the patient, and relevant supporting information must be submitted to the IRB/EC by the Principal Investigator and reviewed and approved by the IRB/EC before the study is initiated. In addition, any patient recruitment materials must be approved by the IRB/EC.

The Principal Investigator is responsible for providing written summaries of the status of the study to the IRB/EC annually or more frequently in accordance with the requirements, policies, and procedures established by the IRB/EC. Investigators are also responsible for promptly informing the IRB/EC of any protocol amendments (see Section 9.6).

In addition to the requirements for reporting all adverse events to the Sponsor, investigators must comply with requirements for reporting serious adverse events to the local health authority and IRB/EC. Investigators may receive written IND safety reports or other safety-related communications from the Sponsor. Investigators are responsible for ensuring that such reports are reviewed and processed in accordance with health authority requirements and the policies and procedures established by their IRB/EC, and archived in the site's study file.

8.4 CONFIDENTIALITY

The Sponsor maintains confidentiality standards by coding each patient enrolled in the study through assignment of a unique patient identification number. This means that patient names are not included in data sets that are transmitted to any Sponsor location.

Patient medical information obtained by this study is confidential and may be disclosed to third parties only as permitted by the Informed Consent Form (or separate authorization for use and disclosure of personal health information) signed by the patient, unless permitted or required by law.

Medical information may be given to a patient's personal physician or other appropriate medical personnel responsible for the patient's welfare, for treatment purposes.

Given the complexity and exploratory nature of the analyses, data derived from exploratory biomarker specimens will generally not be provided to study investigators or patients unless required by law. The aggregate results of any conducted research will be available in accordance with the effective Sponsor policy on study data publication (see Section 9.5).

Data generated by this study must be available for inspection upon request by representatives of the U.S. FDA and other national and local health authorities, Sponsor monitors, representatives, and collaborators, and the IRB/EC for each study site, as appropriate.

8.5 FINANCIAL DISCLOSURE

Investigators will provide the Sponsor with sufficient, accurate financial information in accordance with local regulations to allow the Sponsor to submit complete and accurate financial certification or disclosure statements to the appropriate health authorities. Investigators are responsible for providing information on financial interests during the course of the study and for 1 year after completion of the study (i.e., last patient, last visit [LPLV]).

9. STUDY DOCUMENTATION, MONITORING, AND ADMINISTRATION

9.1 STUDY DOCUMENTATION

The investigator must maintain adequate and accurate records to enable the conduct of the study to be fully documented, including but not limited to the protocol, protocol amendments, Informed Consent Forms, and documentation of IRB/EC and governmental approval. In addition, at the end of the study, the investigator will receive the patient data, including an audit trail containing a complete record of all changes to data.

9.2 PROTOCOL DEVIATIONS

The investigator should document and explain any protocol deviations. The investigator should promptly report any deviations that might have an impact on patient safety and data integrity to the Sponsor and to the IRB/EC in accordance with established IRB/EC policies and procedures.

9.3 SITE INSPECTIONS

Site visits will be conducted by the Sponsor or an authorized representative for inspection of study data, patients' medical records, and eCRFs. The investigator will permit national and local health authorities, Sponsor monitors, representatives, and collaborators, and the IRBs/ECs to inspect facilities and records relevant to this study.

9.4 ADMINISTRATIVE STRUCTURE

Genentech, Inc, a member of the Roche group, is the Sponsor of this study. A clinical research organization (CRO) may provide clinical operations oversight, including but not limited to project management, medical monitoring, site management, data quality support, safety reporting, and regulatory activities as specified in the study management plans. Genentech will provide CRO oversight, develop the database and randomization scheme, and conduct statistical programming and analysis. An IMC and SOC will provide safety monitoring for the study in addition to the ongoing review of safety by the Medical Monitor and safety scientist.

EDC will be utilized for this study. An IxRS will be used to assign patient numbers, randomize patients into study through use of a *permuted block* algorithm, and manage site drug supply. A central laboratory will be used for sample management and storage until shipment to specialty laboratories or Genentech for analysis.

Data reported by patients regarding their symptoms, body temperature, and any use of acetaminophen/paracetamol and/or NSAIDs will be captured using paper diaries.

9.5 PUBLICATION OF DATA AND PROTECTION OF TRADE SECRETS

Regardless of the outcome of a trial, the Sponsor is dedicated to openly providing information on the trial to healthcare professionals and to the public, both at scientific congresses and in peer-reviewed journals. The Sponsor will comply with all requirements for publication of study results. For more information, refer to the Roche Global Policy on Sharing of Clinical Trials Data at the following Web site:

<http://www.rochetrials.com/pdf/RocheGlobalDataSharingPolicy.pdf>

The results of this study may be published or presented at scientific congresses. For all clinical trials in patients involving an IMP for which a marketing authorization application has been filed or approved in any country, the Sponsor aims to submit a journal manuscript reporting primary clinical trial results within 6 months after the availability of the respective clinical study report. In addition, for all clinical trials in patients involving an IMP for which a marketing authorization application has been filed or approved in any country, the Sponsor aims to publish results from analyses of additional endpoints and exploratory data that are clinically meaningful and statistically sound.

The investigator must agree to submit all manuscripts or abstracts to the Sponsor prior to submission for publication or presentation. This allows the Sponsor to protect proprietary information and to provide comments based on information from other studies that may not yet be available to the investigator.

In accordance with standard editorial and ethical practice, the Sponsor will generally support publication of multicenter trials only in their entirety and not as individual center data. In this case, a coordinating investigator will be designated by mutual agreement.

Authorship will be determined by mutual agreement and in line with International Committee of Medical Journal Editors authorship requirements. Any formal publication of the study in which contribution of Sponsor personnel exceeded that of conventional monitoring will be considered as a joint publication by the investigator and the appropriate Sponsor personnel.

Any inventions and resulting patents, improvements, and/or know-how originating from the use of data from this study will become and remain the exclusive and unburdened property of the Sponsor, except where agreed otherwise.

9.6 PROTOCOL AMENDMENTS

Any protocol amendments will be prepared by the Sponsor. Protocol amendments will be submitted to the IRB/EC and to regulatory authorities in accordance with local regulatory requirements.

Approval must be obtained from the IRB/EC and regulatory authorities (as locally required) before implementation of any changes, except for changes necessary to eliminate an immediate hazard to patients or changes that involve logistical or administrative aspects only (e.g., change in Medical Monitor or contact information).

Appendix 1 Schedule of Activities

	Screening (-72 hours to 0 hours)	D1 ^a (Randomization)	D2	D3	D4	D5	D6	D7 (±1)	D8- 13	D14 (±2)	D30 (±7)	D100 (±7)	Unscheduled Visit	Early Discontinuation
Informed consent ^b	x													Complete all assessments for the current day. If a patient discontinues early after Day 7, only a telephone visit is required as the Early Discontinuation visit.
Rapid PCR test or rapid antigen test ^c	x													
Inclusion/exclusion criteria	x													
Medical history and demographics	x													
Seasonal influenza vaccine history	x													
Confirm onset flu symptoms	x													
Pregnancy screening ^d	x													
Concomitant medications ^e	x	x	x	x	x	x	x	x	x	x	x	x	x	
Vital signs ^f	x	x		x				x					x	
Electrocardiogram (12-lead) ^g	x	x ^h		x				x					(x)	
MHAA4549A/Placebo administration ⁱ		x												
Complete physical examination ^j	x												(x)	
Limited, symptom-directed physical examination/symptom assessment ^k		x		x				x					x	
Weight and height ^l	x	x		x				x					(x)	
Adverse events		x	x	x	x	x	x	x	x	x	x	x	x	
Hematology ^m	x			x				x					(x)	
Chemistry panel ^m	x			x				x					(x)	
Coagulation panel ^m		x												
Urinalysis ⁿ	x			x				x					(x)	
██████████ ██████████		x		x		x		x					(x)	

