3.4 OUTCOME MEASURES

3.4.1 Primary Outcome Measures

- Incidence, nature, and severity of adverse events and clinical laboratory abnormalities (graded according to the Division of Acquired Immunodeficiency Syndrome [DAIDS] Toxicity Grading Tables for Clinical Abnormalities) associated with the administration of MHAA4549A to patients with influenza A as measured by changes in vital signs, physical findings, *and* clinical laboratory results

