4.6.4 Study Completion/Early Discontinuation

Patients who complete all study visits through Day 100 are considered to have completed the study. All patients who discontinue from the study early will be asked to complete all assessments for the *current day*. *If a patient discontinues after Day 7, only a telephone visit is required as the Early Discontinuation visit.* Please see Schedule of *Activities* provided in [Appendix 1](#) for assessments performed at the Study Completion *and* Early Discontinuation visit.

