6.4 PRIMARY SAFETY ANALYSES

The safety analyses will include all randomized patients who received study drug, with patients grouped according to the treatment actually received. Safety parameters to be evaluated include adverse events (including deaths, serious adverse events, discontinuations due to adverse events, and the incidence and severity of adverse events), clinical laboratory tests, vital signs, and ECGs. All collected adverse event data will be listed by study site and patient number. All adverse events that occur on or after treatment on Day 1 will be summarized for each treatment group by mapped term, appropriate thesaurus levels, body system, and event within each body system, and toxicity grade. In addition, all serious adverse events, including deaths, will be listed separately and summarized. Serious adverse events caused by a protocol-mandated intervention (e.g., invasive procedures such as biopsies, discontinuation of medications) that occur between consent and first dose of study medication will be listed separately.

Laboratory data with values outside of the normal ranges will be identified. In addition, select laboratory data will be summarized by treatment group using descriptive summary statistics.

The absolute and percentage changes from baseline in vital sign parameters will be computed, and changes deemed clinically significant by the Investigator will be noted. Appropriate descriptive summary statistics will be provided for all vital sign parameters.

The prevalence (baseline) of ATA will be reported and correlation with PK, safety, efficacy, and *biomarker* endpoints will be analyzed as data allow.

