Appendix 1 (cont'd) Schedule of *Activities*

	Screening (-72 hours to 0 hours)	D1 ^a (Randomization)	D2	D3	D4	D5	D6	D7 (±1)	D8- 13	D14 (±2)	D30 (±7)	D100 (±7)	Unscheduled Visit	Early Discontinuation
Influenza antibodies (HAI) ^p		x						x						Complete all assessments for the current day. If a patient discontinues early after Day 7, only a telephone visit is required as the Early Discontinuation visit.
Anti-MHAA4549A antibodies (ATA) ^p		x												
Serum for MHAA4549A PK measurements ^q		x		x		x		x					(x)	
████████████████████		x		x		x		x					(x)	
Telephone visit to assess safety			x							x	x	x		
Symptom Diary ^r		x	x	x	x	x	x	x	x	x				

AE= adverse event; D= day; HAI= hemagglutinin inhibition; PCR= polymerase chain reaction; PK= pharmacokinetic.

Notes: Days 1, 3, 5, 7, *unscheduled (shaded)*, and *early discontinuation (if applicable)* will be clinic visits.

Xs within parentheses, i.e., (X), indicate optional assessments.

Patients who are unable to return to the clinic should be contacted by phone to: 1) ascertain health status, 2) record adverse event information, and 3) ask that the diary be completed and returned.

^a All assessments on Day 1 should be performed prior to study drug administration.

^b Informed consent must be obtained from all patients.

^c Sample collection may involve a nasal swab or a nasopharyngeal swab, depending on the diagnostic platform *at the site*.

^d A urine pregnancy test should be collected only for women considered by the investigator to be of childbearing potential, see exclusion criteria. This result must be available within 48 hours prior to study treatment. If urine testing is not available at the site, blood already collected from an existing sample may be tested for pregnancy.

^e Concomitant medications should be recorded for 30 days prior to screening, through the study completion/early discontinuation visit. See exclusion criteria for prohibited therapies. Patients should report to study site all concomitant medications taken at home.

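### The Early Discontinuation visit has no fixed assessment set, so an exit on Day 2, 4, 5 or 6 requires no vital signs, ECG or safety laboratory tests

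*Combined protocol and SAP*

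**What the plan says.** The Early Discontinuation column of Appendix 1 contains one instruction in place of a list: "Complete all assessments for the current day. If a patient discontinues early after Day 7, only a telephone visit is required" as the exit visit. Section 4.6.4 says "All patients who discontinue from the study early will be asked to complete all assessments for the" current day, gives the same telephone rule after Day 7, and refers back to Appendix 1 for the assessments. The notes to Appendix 1 add that "early discontinuation (if applicable)* will be clinic visits".

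The measurements at issue are part of the primary outcome. Section 3.4.1 defines that outcome as adverse events and laboratory abnormalities "as measured by changes in vital signs, physical findings" and clinical laboratory results. Section 6.4 lists laboratory tests, vital signs and ECGs as safety parameters in their own right, beside adverse events and "discontinuations due to adverse events".

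In Appendix 1 the rows "Electrocardiogram (12-lead) ^g" and "Limited, symptom-directed physical examination/symptom assessment ^k", and the vital signs row, are marked on Days 1, 3 and 7. The row "Chemistry panel ^m", with hematology and urinalysis, is marked at screening and on Days 3 and 7. Adverse events and concomitant medications are marked on every day.

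**The concern.** The content of the exit visit depends on the calendar day on which the patient happens to leave. On Days 2, 4, 5 and 6 the instruction points to a column with no objective safety measurement. A patient may be called to the clinic with nothing scheduled to measure.

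Questioning about adverse events does not fully replace the missing tests:

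- Section 1.2.2.3 reports ALT, AST and amylase elevations as the most common treatment-emergent events in the challenge study. Section 5.7 recognises that such elevations can be asymptomatic in influenza.
- Sections 5.3.5.5 and 5.3.5.6 make a laboratory or vital-sign abnormality reportable as an adverse event only if a repeat assessment verifies it and a further criterion is met. An abnormal Day 3 value in a patient who leaves on Days 4 to 6 has no repeat guaranteed at exit.
- The liver-injury event of special interest (Sections 5.2.3 and 5.3.5.7) cannot be identified without transaminase results.
- Section 4.6.1 rules out follow-up after consent is withdrawn, so the exit visit may be the last chance to measure anything.

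**Working it through.** **1. The plan's own figure.** Section 6.1 plans 141 patients to obtain 120 evaluable, with 15% dropout. 120 / (1 − 0.15) = 141.2, which agrees with about 141. Planned dropouts: 141 − 120 = 21. This is the only dropout figure in the documents, and its timing is not given.

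**2. Appendix 1 read by column.**

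| Day | Vital signs | ECG | Limited examination | Hematology, chemistry, urinalysis | Adverse events, medications |
|---|---|---|---|---|---|
| 1 | yes | yes | yes | no | yes |
| 2 | no | no | no | no | yes |
| 3 | yes | yes | yes | yes | yes |
| 4 | no | no | no | no | yes |
| 5 | no | no | no | no | yes |
| 6 | no | no | no | no | yes |
| 7 (±1) | yes | yes | yes | yes | yes |
| Unscheduled | yes | optional | yes | optional | yes |

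Day 5 also has serum PK and rows with redacted labels. No text links the Unscheduled column to early discontinuation.

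**3. Days affected.** Days 2, 4, 5 and 6 are 4 of the 6 days from Day 2 to Day 7 (67%). If a Day 6 exit is handled as the Day 7 visit under its ±1 day window, the count is 3 of 6 (50%). These are shares of days, not of patients.

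**4. What a leaver already has.**

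- Leaves after dosing on Day 1, or on Day 2: post-infusion vital signs (within 1 hour, note f) and an ECG at 1 to 3 hours post-dose (note h), if the patient stayed for them. No post-dose hematology, chemistry or urinalysis.
- Leaves on Days 4 to 6 after attending Day 3: one complete post-dose set from Day 3, but no exit or confirmatory values.

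**5. Patients affected, by assumption.** All 21 dropouts are treated as patients leaving the study.

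- Constant rate over 100 days: expected leavers by day t = 141 × (1 − 0.85^(t/100)). For t = 7 this is 1.6. Summing the daily increments for Days 2, 4, 5 and 6 gives 0.9. For Days 1 and 2 together, 141 × (1 − 0.85^0.02) = 0.46.
- A share f of the 21 leaving evenly over Days 2 to 7: affected = 21 × f × 4/6, or 21 × f × 3/6 with the Day 6 window.

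| f | Leavers, Days 2–7 | Affected (4/6) | Affected (3/6) |
|---|---|---|---|
| 10% | 2.1 | 1.4 | 1.1 |
| 25% | 5.3 | 3.5 | 2.6 |
| 50% | 10.5 | 7.0 | 5.3 |
| 100% (ceiling) | 21 | 14 | 10.5 |

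At f = 25%, Day 2 alone accounts for 21 × 0.25 / 6 = 0.9 patients. Sample size and Table 5 are unaffected in every case.

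**The case against.** The strongest reply is that other sections cover the exit and that very few patients are involved. Section 5.1 makes the investigator responsible for a clinical assessment before a participant is discharged from the study. Section 4.5.5 calls for limited examinations at subsequent visits. Section 4.5.8 allows unscheduled ECGs, Section 5.3.5.5 asks for prompt repeats of abnormal laboratory results, and Section 5.5.1 requires each adverse event to be followed until it resolves or is stable, unless the patient is lost or withdraws consent. A patient who withdraws consent cannot be obliged to undergo a panel. Stopping the infusion (Section 4.6.2) is also separate from leaving the study, so a reaction does not by itself end follow-up.

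Much of this stands. An examination or clinical assessment at exit is supported by the text, and the expected numbers are small. But none of these sections requires vital signs, an ECG or laboratory tests at the exit visit. The repeat and follow-up rules apply only once an abnormality or event is known.

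A reader might infer that most patients who leave in the first week give no exit safety data, or that they drop selectively out of the post-dose summaries. The documents support neither. Adverse events and medications are collected on every day, and adverse events are reported up to the Early Discontinuation visit (Section 5.3.1). Leavers on Days 4 to 6 who attended Day 3 contribute a post-dose set. A share of days is not a share of patients. Nothing in the documents shows that early leavers are more likely to have abnormal results. The no-imputation statement in Section 6.5 belongs to the efficacy analyses.

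**Conclusion.** The point holds as a limited gap in the exit assessment. As written, the rule requires no vital signs, ECG or safety laboratory tests at an exit on Day 2, 4, 5 or 6, and no post-dose hematology, chemistry or urinalysis for anyone who leaves after dosing on Day 1 or on Day 2. That second group is the main loss. For Days 4 to 6 the loss is of exit and confirmatory values, provided the patient attended Day 3.

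The size rests on assumed dropout timing: about 1 patient in the trial at a constant rate, and 3 to 4 if a quarter of dropouts fall evenly on Days 2 to 7 (2 to 3 if the Day 7 window covers Day 6). This does not threaten the trial. It is worth correcting because safety is the primary objective, the plan counts on only 40 evaluable patients per arm, and the change is small.

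**What to change.** In the Early Discontinuation column of Appendix 1 and in Section 4.6.4, replace the current-day rule for any post-dose discontinuation through Day 7. Where the patient agrees, require the safety assessments already listed for Day 7: vital signs, ECG, limited examination, hematology, chemistry, urinalysis, adverse events and concomitant medications. Keep the telephone-only rule after Day 7.

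The cost is one line in each place and one extra set of existing tests for a few patients, at a visit that the notes already make a clinic visit where applicable. No analysis or sample-size change follows.
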